4.4 Baseline and Demographic Characteristics

No formal comparison between treatment groups on baseline and demographic characteristics will be done. Unless specifically stated in the relevant section, analysis will be done on the mITT Population.

4.4.1 Demography Characteristics

Demographics will be summarised by treatment group and overall. This will include age, ethnicity, gender, race, employment status, height (cm), weight (kg), BMI (kg/m²).

Summaries will be produced using the mITT and the Safety Population.

Note:

- Age, height, weight, BMI and employment status recorded at Visit 1 will be presented.

CONFIDENTIAL

Sponsor:	Zambon S.p.A.	Protocol Number:	Z7224L01
----------	---------------	------------------	----------

4.4.2 Smoking and Alcohol Status

Smoking status at Screening (non-smoker, former smoker or current smoker), will be presented by treatment group and overall for the mITT Population. Former smoker will be further characterised summarising time from last cigarette (years) and number of pack-years.

Alcohol Status (Alcohol consumer: Yes or No) at Screening will be presented by treatment group and overall, along with summaries of alcohol units per week for alcohol consumers.

Notes:

- For former smokers, time from last cigarette (years) will be calculated as (screening date – date of last cigarette)/365.25;
- In order to calculate the time from last cigarette, the following rules will be applied for partial dates of the last date of smoking:
 - if only the day is missing, the first day of the month will be assumed;
 - if the day and the month are missing, then the first day of the year will be assumed.

4.4.3 Non-CF Bronchiectasis History

The following variables will be summarised for the mITT Population by treatment group and overall:

- Time since diagnosis of non-CF bronchiectasis (years);
- Diagnostic technique used (computerised tomography [CT] or high resolution CT: Yes or No);
- Number of lobes affected (1, 2, 3, more than 3);
- Underlying cause of the bronchiectasis;
- Number of NCFB pulmonary exacerbations requiring oral antibiotics in the last 12 months before Screening;
- Number of NCFB pulmonary exacerbations requiring intravenous antibiotics in the last 12 months before Screening;
- Previous usage of colistimethate sodium/colistin;
- Having at least 1 positive sputum culture for *P. aeruginosa* before Screening.

Notes:

- Time since diagnosis of NCFB (years) will be calculated as (date of Visit 1 – date of diagnosis of NCFB)/365.25;
- In order to calculate the time since diagnosis of NCFB, the following rules will be applied for partial dates of the date of diagnosis of NCFB:
 - if only the day is missing, the first day of the month will be assumed;
 - if the day and the month are missing, then the first day of the year will be assumed.

CONFIDENTIAL

Sponsor:	Zambon S.p.A.	Protocol Number:	Z7224L01
----------	---------------	------------------	----------

4.4.4 Past or Concomitant Relevant Diseases, Diagnoses or Surgeries

Past or concomitant relevant diseases, diagnosis or surgeries will be summarised by system organ class (SOC) and preferred term (PT), by treatment group and overall using the mITT Population.

Notes:

- Past or concomitant relevant Diseases, Diagnoses or Surgeries will be coded according to the Medical Dictionary for Regulatory Activities (MedDRA) version 19.1 or higher;
- Past relevant Diseases, Diagnoses or Surgeries are defined as records in the Medical History eCRF form which are not ongoing at Visit 1;
- Concomitant relevant Diseases, Diagnoses or Surgeries are defined as records in the Medical History eCRF form which are ongoing at Visit 1;
- Terms will be displayed in descending overall frequency (and then alphabetically) of SOCs and in descending overall frequency (and then alphabetically) of PTs within each SOC.

4.4.5 Spirometry at Visit 1 and Pre-Dose at Visit 2

The following spirometry parameters will be summarised by treatment group and overall:

- FEV₁ (L);
- Predicted FEV₁ (%);
- FVC (L);
- Predicted FVC (%).

Spirometry results assessed at Visit 1 and at Visit 2 Pre-dose will be summarised using summary statistics for continuous variables. Summaries will be provided for the mITT and for the Safety Population. Results for the Safety Population will be presented along with summaries for spirometry parameters assessed during Visits 3 – 7, inclusive.

More details of the analysis are reported in [Section 4.8.2](#).

4.4.6 Haematology, Clinical Chemistry and Renal Function Parameters at Visit 1

Haematology, clinical chemistry and renal function parameters assessed at Visit 1 will be listed.

More details of the analysis are reported in [Section 4.8.4](#).

4.4.7 Vital Signs at Visit 1

Respiratory rate (breaths per minute), heart rate (beats per minute), systolic and diastolic blood pressure (mmHg) and body temperature (°C) assessed at Visit 1 will be listed.

More details of the analysis are reported in [Section 4.8.5](#).

4.4.8 Physical Examination at Visit 1

Physical Examination findings collected at Visit 1 will be listed.

CONFIDENTIAL

Sponsor:	Zambon S.p.A.	Protocol Number:	Z7224L01
----------	---------------	------------------	----------

More details of the analysis are reported in [Section 4.8.6](#).

4.4.9 12-Lead ECG at Visit 1

The 12-lead ECG overall interpretation at Visit 1 will be listed.

More details of the analysis are reported in [Section 4.8.7](#).

4.4.10 Pregnancy Test

Results from the dipstick urine pregnancy test for women of child-bearing potential will be listed only.

4.4.11 Presence of *P. aeruginosa* in Sputum at Visit 1

Number and percentage of subjects with presence of [CCI] collected at Visit 1 will be reported for the mITT Population. Subjects with results <20CFU/mL will be considered as negative based on the central lab specifications. The local laboratory result will just record presence or absence of *P. aeruginosa* for eligibility purposes only. The number and percentage of subjects with presence of [CCI] as collected in the eCRF will be presented.

4.4.12 [CCI] and [CCI]

The [CCI] total score and domain scores and the [CCI] domain scores at Visit 2 (see [Sections 4.7.6.2](#) and [4.7.6.9](#) for further details regarding the calculation of the [CCI] and [CCI]) will be summarised by treatment group and overall using the mITT Population and the PP Population for [CCI] and the mITT Population only for [CCI] (see [Section 4.7.5](#)). Results will be presented along with summaries for results at Visits 3 – 7, inclusive.

4.5 Exposure

4.5.1 Number and Duration of Inhaled Doses

An inhaled dose is defined as any complete or partial dose of IMP that the subject inhaled either at the investigational site or at home (excluding doses ≤12.5% as recorded in the [CCI] logging system and any final dose recorded in the [CCI] logging system that is more than 14 days after the penultimate dose in the [CCI] logging system where Visit 7 was split due to Covid-19, as described in [Section Error! Reference source not found.](#)).

For doses administered at the investigational site, inhaled doses are all doses with a date of administration filled in the “IMP administration under clinical supervision” eCRF page. Complete doses are those recorded as complete in the eCRF. Partial doses are those recorded as non-complete in the eCRF.

For doses administered at home, inhaled doses are all doses with a date and time of administration recorded in the [CCI] logging system and dose different than “Null” or “≤12.5%”.

The overall number of inhaled doses either at the investigational site or at home will be summarised along with their duration. For doses administered at the investigational site only, the number of complete and partial doses will also be reported.

CONFIDENTIAL

Sponsor:	Zambon S.p.A.	Protocol Number:	Z7224L01
----------	---------------	------------------	----------

Summaries will be presented for the Safety and mITT Populations.

Notes:

- All the doses will be recorded in the CCI logging system, regardless of being administered at the investigational site or at home. Doses administered at home are those not recorded in the eCRF. In case of any inconsistencies between eCRF and CCI data, the CCI data will be used in the analysis. While missing date/time of doses might be present in the eCRF, CCI data are expected to be complete.

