9.2. ADHERENCE WITH IMP DOSING REGIMEN

The Investigator will assess the subjects' adherence with the IMP dosing regimen on an ongoing basis by the data downloaded from the **CCI** device into a data analyser installed in laptops provided by the Sponsor.

Information on data download from the **CCI** logging system is given in [Section 9.1.5](#).

The Investigator will also assess the amount of IMP dispensed, used (i.e. returned open vials) and not used (i.e. returned, unopened vials) at all clinical visits, starting with Visit 2 (first dose) up to the day of the last dose (Visit 7/End of Treatment).

IMP inventory and accountability records will be maintained within IWRS.

In the event that adherence is less than approximately 80% at any visit, adherence will be discussed with the subject and appropriate re-training will be given by site staff.

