	Exclusion criteria #13 (as re-numbered) has been amended from “known or suspected to be allergic or unable to tolerate colistimethate sodium or other polymixins (intravenous or inhaled) including evidence of bronchial hyperreactivity” to “known or suspected to be allergic or unable to tolerate colistimethate sodium (intravenous or inhaled) or other polymixins, including evidence of bronchial hyper-reactivity following inhaled colistimethate sodium”.	Clarification of exclusion criterion.
Section 8.2: Visit 2 - Randomisation Visit (Day 0)	Wording has been added to allow patients to continue in the study without pre-bronchodilator use prior to IMP administration.	As stated above, this requirement has been removed due to feedback that, as many patients can tolerate the IMP without it, then the mandated use or a short-acting inhaled bronchodilator prior to IMP administration is an unnecessary burden on patients who would prefer not to use it. The use of the bronchodilator is to aid tolerability not to improve efficacy.
	The timing for the administration of any pre-bronchodilator (at least 10 minutes prior to IMP administration) and post-IMP administration spirometry assessment (30 ± 10 minutes) have been amended.	The timings have been amended to reflect a more practical timeline and to indicate acceptable assessment ranges.
Section 8.5: Visit 7 (12 Months ± 1 Week); End of Treatment	The timing for the administration of any pre-bronchodilator (at least 10 minutes prior to IMP administration) and post-IMP administration spirometry assessment (30 ± 10 minutes) have been amended.	The timings have been amended to reflect a more practical timeline and to indicate acceptable assessment ranges.
	The reference to CCI devices being returned via CCI has been deleted.	This study procedure/logistic is not working effectively and a new work instruction for the return of the CCI device is currently being created.
Section 9.1.6: Safety Evaluations	The timing for the spirometry assessments prior to the administration of any pre-	The timings have been amended to reflect a more practical timeline and to indicate

	bronchodilator (at least 10 minutes prior to IMP administration) and post-IMP administration (30 ± 10 minutes) have been amended.	acceptable assessment ranges.

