3.5.4 Per-Protocol Population

The Per-Protocol Population (PP) will include all mITT subjects who were considered compliant with study drug administration (i.e. had an adherence of at least 80%) and who had no major protocol deviations that were considered as potentially impacting the efficacy results.

Major protocol deviations might include, but are not limited to, subjects taking a not-permitted concomitant medication, the IMP not being administered during the trial as defined in the protocol, subjects receiving a treatment different than the one assigned by randomisation. Categories of protocol deviations and additional details are reported in Section 4.10. The exact definition of major protocol deviations impacting the efficacy results will be discussed by the

CONFIDENTIAL

Sponsor:	Zambon S.p.A.	Protocol Number:	Z7224L01
----------	---------------	------------------	----------

study team during the blind review of the data and described in the Blind Data Review and Analysis Sets Report.

Results of the primary and relevant secondary efficacy endpoints analyses conducted for the PP will be considered as supportive.

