4.1.9 Date of First/Last IMP Dose

The date of first IMP dose is the earliest date of IMP dose considering both the eCRF and the recordings from the CCI logging system.

The date of last IMP dose is derived as follows. Where CCI data is available for the subject, the date of last IMP dose will be defined as the latest date from the CCI logging system, with the following exception. Due to the Covid-19 pandemic, for some subjects, Visit 7 was split into a remote phone call (at the scheduled time of treatment completion), followed by an in-clinic visit (for the purpose of collecting pre-dose and post-dose spirometry data to test for bronchospasm). In such cases, the scheduled study treatment period was completed at the time of the remote Visit 7 phone call, but an additional IMP dose was given at the time of the in-clinic Visit 7. In these circumstances, the latest date from the CCI logging system will be compared to the penultimate date from the CCI logging system and, if the latest date is more than 14 days after the penultimate date (latest date – penultimate date >14), the CCI logging system data will be used taking into consideration the penultimate IMP dose as the date of last IMP dose. The date of last IMP dose will be defined as the date of last IMP administration as entered on the End of Study eCRF form only when CCI data is unavailable.

Any inconsistency between eCRF and CCI logging system data will be discussed before the database lock.

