4.5.4 Adherence

Adherence will be calculated overall.

The evaluation of adherence will be based on the following formula:

- Adherence (%) = (# Total Inhaled Doses / # Scheduled Doses)*100.

The total number of inhaled doses of IMP will be computed as described in Section 4.5.1. In cases where, due to the Covid-19 pandemic, the final dose registered on the CCI device is the dose given at the in-clinic part of a split Visit 7 for the purposes of bronchospasm testing, any dose on the CCI that is later than the date of last IMP administration as entered on the End of Study eCRF form will not be counted as an inhaled dose for the calculation of IMP adherence.

The scheduled doses will be computed as 2 times the total number of days from Visit 2 to the end of period date, i.e. (End of period date – date of Visit 2) + 1.

For the overall adherence, the end of period date will be the date of the last inhaled dose of IMP, based on the latest of the last dose recorded in the CCI download (with the exceptions

CONFIDENTIAL

Sponsor:	Zambon S.p.A.	Protocol Number:	Z7224L01
----------	---------------	------------------	----------

noted above relating to split Visit 7's) or the date of the last dose of IMP recorded in the End of Study form in the eCRF.

Adherence will be summarised by treatment group and overall for the mITT Population, presenting descriptive statistics for continuous variables and absolute and relative percentages of subjects considered to be adherent, i.e. with a least 80% of adherence.

An additional summary displaying the number and percentage of subjects in the following categories will also be presented by treatment group:

- <60%;
- 60 to <70%;
- 70 to <80%;
- 80 to <90%;
- ≥90%.

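### Doses missing from the nebuliser log count as doses not taken when the eCRF last-dose date runs past the log, so adherence can fall below 80% through lost data alone

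*SAP*

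**What the plan says.** **Numerator.** SAP 4.5.1 separates two kinds of dose. For home dosing, "For doses administered at home, inhaled doses are all doses with a date and time of administration recorded in the" device's logging system, leaving out null records and those of 12.5% or less. For clinic dosing, "inhaled doses are all doses with a date of administration filled in the" supervised-administration page of the eCRF. If the two sources disagree, the log prevails. The section adds that log "data are expected to be complete".

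**Denominator.** SAP 4.5.4 schedules two doses a day from Visit 2 to an end date that is "based on the latest of the last dose recorded in the" device download or on the End of Study form.

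**Last-dose date.** SAP 4.1.9 takes the latest logged date. It uses the date "as entered on the End of Study eCRF form only when" log data are unavailable. A separate exception deals with Visit 7 split by Covid-19. Inconsistencies between log and eCRF are to be discussed before lock.

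**Use of the result.** SAP 3.5.4 admits to the per-protocol set subjects who "had an adherence of at least 80" per cent and have no relevant major deviation. SAP 3.5.2 and 4.7.4.3 apply the same cut-off to the adherent subgroup of the mITT.

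**Other data held.** Protocol 9.2: "The Investigator will also assess the amount of IMP dispensed, used (i.e. returned open vials) and not used" at the clinic visits. Protocol 9.1.5 has the device downloaded to a site laptop during the trial and again after Visit 7.

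**The concern.** The numerator depends entirely on the log for home doses, but the denominator can be extended by the eCRF. If the log is silent for a period that the eCRF shows as treated, nothing is added above the line while two doses a day are added below it. Lost data then look the same as skipped doses.

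The SAP recognises in 4.1.9 that log data may be unavailable, yet repairs only the date and not the dose count. For a partial log, 4.1.9 and 4.5.4 also end treatment on different days.

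At stake are the reported adherence distribution, the dose counts and Exposure Days (both shown for the Safety and mITT populations), and membership of the per-protocol and adherent sets. Those sets are supportive, but adherence has mattered in this programme. Protocol Section 3 reports that in the predecessor trial time to exacerbation gave p = 0.11 overall and p = 0.028 in the adherent patients. The SAP addendum also stresses internal consistency for an application resting on one pivotal study. A set chosen partly on whether data were retrieved is weaker support.

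**Working it through.** The plan gives no figure that depends on this rule, so there is none to reproduce. The check applies the SAP's formula to constructed cases.

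**Inputs**
- Adherence = 100 × inhaled doses / scheduled doses (SAP 4.5.4).
- Scheduled doses = 2 × (end date − Visit 2 date + 1) (SAP 4.5.4).
- Cut-off: 80% (SAP 3.5.4, 4.7.4.3).
- Treatment lasts 12 months (Protocol 6.2), taken here as 366 days inclusive. This is an assumption for illustration.
- Supervised clinic doses: first dose at Visit 2 and last at Visit 7 (Protocol 8.2, 8.5), so about 2.
- The End of Study form is assumed to carry the true last-dose date, day 366, and true adherence *t* is assumed constant.

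**Scheduled doses and cut-off.** 2 × 366 = 732; 0.80 × 732 = 585.6 doses.

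**No log.** 2/732 = 0.27%.

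**Log covering the first *L* days.** Adherence = 100 × (*t* × 2*L*)/732.

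| Log to day | *t* = 100% | *t* = 90% |
|---|---|---|
| 183 | 50.0% | 45.0% |
| 270 | 540/732 = 73.8% | 486/732 = 66.4% |
| 274 | 74.9% | 67.4% |
| 304 | 83.1% | 74.8% |
| 335 | 91.5% | 82.4% |

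If the supervised Visit 7 dose is also counted from the eCRF, one dose is added (541/732 = 73.9% for the perfect user at day 270), which changes no conclusion here.

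**Largest lost tail that still passes.** The log must cover *L* ≥ 0.80 × 366/*t* days.

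| True adherence | Log days needed | Days that can be lost |
|---|---|---|
| 100% | 293 | 73 |
| 95% | 309 | 57 |
| 90% | 326 | 40 |
| 85% | 345 | 21 |
| 80% | 366 | 0 |

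**Disagreement between exposure measures.** With a log to day 270, the 4.1.9 date gives an extent of exposure of 270 days, while the adherence denominator runs for 366, a difference of 96 days. (The cross-reference in 4.5.3 is broken; 4.1.9 is the section that defines the date.) With no log, the subject has about 2 Exposure Days under 4.5.2 but an extent of exposure of about 366 days, because 4.1.9 then falls back on the eCRF date.

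**The case against.** The strongest reply is that the SAP nowhere says that a missing log is to be scored as skipped doses. That is correct: it is the literal result of the formula. SAP 4.11 imputes nothing unless stated and shows subjects with missing data in a separate category, so a subject with no log could be reported as missing. Pre-lock discussion (4.1.9), blind review of critical missing data (4.11) and pre-unblinding decisions on exclusions (4.10.1) could each have caught such cases. But none of these sets a rule, and a subject whose adherence is missing has still not been shown to reach 80%.

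Several stronger readings are tempting, and the documents do not support them:

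- **Any shortened log excludes the subject.** It does so only if adherence drops below 80%. If the eCRF date is blank or no later than the log, a lost tail does not lower adherence. In the time-to-event analysis of SAP 4.7.6.1, adherence is taken only to the first exacerbation, so later log loss need not matter.
- **4.1.9 contradicts 4.5.1.** The remark about completeness compares date and time fields in the log with those in the eCRF. It does not promise that every log was retrieved.
- **Logs were in fact lost.** The protocol's summary of key changes says of one device-return route: "This study procedure/logistic is not working effectively". The same entry says a new instruction was being prepared, and on-site download is the main route. No lost data are reported.
- **Visit downloads are ignored.** They come from the same log, and the SAP does not confine itself to the final download. It simply does not say that they fill gaps.
- **Losses concentrate in withdrawn subjects.** This is plausible but not shown. Devices are brought to every visit (Protocol 11.2), and withdrawn subjects are to return study materials (Protocol 14, partly redacted).
- **A share of the 377 randomised subjects is misclassified.** No share is given, and some subjects with poor logs would still pass or would truly be non-adherent.

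Log-based adherence is also the protocol's own choice. Vial counts are cruder: an opened vial is not an inhaled dose, and they cannot apply the 12.5% rule.

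**Conclusion.** The point stands in limited form. The stated numerator and denominator use different sources, and where the log is absent or ends before the eCRF last-dose date the formula gives a wrong answer: about 0.3% with no log, and 73.8% for a perfect user logged to day 270 of 366. Such a subject may be left out of the per-protocol and adherent-mITT analyses. Exclusion is not automatic, since a perfect user tolerates about 73 lost days and a 90% user about 40.

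These figures rest on a 366-day course, constant use, and a correct eCRF date later than the end of the log. The reach is the adherence and exposure summaries and the supportive analyses: the primary rate, plus the two secondary endpoints that SAP 4.7.5 carries into the per-protocol set. The primary mITT result is untouched. How many subjects are concerned cannot be worked out from the documents. It is worth correcting because the remedy is cheap.

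**What to change.** Amend SAP 4.5.1 and 4.5.4 as follows.

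1. Where the log is absent or has a documented gap (device lost or replaced, download failed), first use all available downloads, including visit downloads and any replacement device.
2. Remove any period still without log data from both numerator and denominator. The perfect user logged to day 270 then scores 540/540 = 100%, and the 90% user 486/540 = 90%.
3. If no period remains, class adherence as not evaluable, report the number by arm, and do not place the subject in the below-60% category.
4. Use one last-dose date in 4.1.9, 4.5.3 and 4.5.4.
5. Use returned-vial counts only as a sensitivity check.
6. Rerun the per-protocol and adherent analyses under this rule. The addendum states that the database is locked and the study unblinded, so SAP Section 1 requires these to be marked post hoc.

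The cost is SAP wording and some programming on data that the protocol already collects. The drawback is that adherence for these subjects rests on a shorter observed period, and use during the unlogged time is assumed rather than seen.
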